## **E. Quality Assurance / Monitoring**

We have signed a formal data use agreement specifying the terms of data use and protection. Data collection and sharing for this project was funded by the KUADC (NIH P30AG035982). KUADC has a designated Data Management Core that provides support for data collection, management and secure storage. All data are entered on standardized forms during the clinical visits and entered into a central database. Data are doubly entered to minimize data entry errors. Upon completion, we conduct logic, edit, and range checks. Queries are sent to the study coordinator for resolution. Data are downloaded and locked in a secure dataset. The database is backed up in an off-site location. Data security is ensured by managing all data on a secure server that has role-based access that is password protected. All files that are modified are backed up daily, with complete backups of the server on a weekly basis. Confidentiality is strictly safeguarded by HIPAA-compliant standards and all data are stored in a HIPAA compliant manner. All paper records will be kept in locked files in the research offices to which only our research personnel have access and filed by number in accordance with professional standards of privileged information. Any information on the subjects which may be shared will only be identifiable through a code number and will not have any personal information attached. Empathetic and professional staff mitigates risk of embarrassment.

There are no plans to have ongoing third party monitoring.

## **V. Data Analysis and Reporting**

### **Statistical and Data Analysis:**

**Data Analysis:** We will use a multi-level model to evaluate the change in our outcome variables across three time points. Level 1 is time of observation (baseline, mid-study, follow up). Level 2 is the individual (with or without MCI), and Level 3 is the level of the dyad. This model includes the non-independence in the estimation of the two members of the dyad as well as repeated observations for each individual. This model also allows us to compare whether individuals with MCI are equally or less responsive to the intervention than the study partners within the context of the dyadic relationship. Constraining estimates to be equivalent provides a test of the significance of the difference in the estimates between the MCI patients and the study partners. We are primarily interested in the change in outcome measures (listed below) from pre-intervention to post-intervention (i.e., is the intervention effective), thus we are testing for a growth model with an intercept change, indicating a mean change after the intervention, this type of model can estimate discontinuous processes with longitudinal data. With regard to the multiple time points, we hypothesize an improvement in outcomes from baseline to mid-point and a maintenance effect from mid-point to follow up. Outcomes are (1) average daily sitting time (2) number of sitting bouts >30 min (3) insulin and glucose, adjusting for baseline values and relevant covariates (disability status, medications, age, education, etc.). **Outcome:** Milestones for achieved **feasibility** include successful recruitment and retention of participants, 10% or less of technological failures, rate of participant concerns addressed by phone and at home visits, acceptability of the intervention to participants (measured by questionnaires HI3), and few adverse events. Effectiveness of the intervention will be evaluated based on change of moderate effect size in the average amount of time spent in sitting and duration of sitting bouts as demonstrated in previous studies. Two previous intervention studies reported a decline in sitting time of about 3 - 4%. We will use this range as our target for success.

**Study results to participants:** Participants will learn their individual results from activity monitoring as part of the intervention at home visit 1 and clinical visit 2. These results are used as educational and motivating agents to modify the participants' behavior.

**Publication Plan:** Our plan is to use the results from this pilot study to support an NIH R21 application to fund a larger RCT of our intervention to reduce sitting time. We will publish results in a peer reviewed manuscript.

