Interventions targeting sedentary behavior can effectively reduce sitting time (average 42 min/day), but few studies have evaluated whether these reductions result in clinically meaningful outcomes and none have been conducted in older adults with MCI. **We propose a feasibility study of a 12-week home based behavioral intervention to reduce sitting time among sedentary older adults with MCI and their caregivers.** The intervention is designed to break up prolonged bouts of sitting and replace sitting behavior with standing and light or moderate intensity activities associated with improved cognitive performance among people at risk for AD. Our proposed intervention adds innovative elements that are empirically rigorous compared to previous studies: 1) it uses objectively assessed electronic postural monitoring, 2) it provides electronic feedback to promote sitting times <30 minutes, 3) it assesses insulin sensitivity and glycemic control which are sensitive to changes in sitting after a short duration and which few previous interventions have measured, 4) it is conducted in the home and targeted to individual habits and physical environments that reinforce sitting behaviors, 5) it targets sedentary older adults with MCI, which has not been done before, and 6) it capitalizes on the caregiver/patient dyad to help improve adherence to the behavioral change regimen.

**Specific Aim 1: Determine feasibility of a 12-week home and telephone based intervention in older adults with mild cognitive impairment targeting both the impaired individual and their study partner to help initiate and maintain behavior change.** We will recruit KUADC registry participants with MCI and their caregivers (as study partners). Behavioral interventions are more effective when there is built in social support. We will evaluate feasibility in terms of successful recruitment and retention of participants, 10% or less of technological failures, rate of participant concerns addressed by phone and at home visits, acceptability of the intervention to participants (measured by questionnaires during home visits).

**Specific Aim 2: Determine whether a 12-week home and telephone based intervention results in reduced total sitting time and shorter bouts of sitting in older adults with MCI and their caregivers.** Electronic postural monitors will record sitting time for a duration of one week at three time

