points (pre-intervention, mid-intervention, and post-intervention). The intervention includes 1) feedback from baseline monitoring, 2) educational and goal setting session with the participants and research staff, 3) wrist worn monitors that alert wearers to sitting times >30 minutes, 4) home and telephone visits to address physical, psychological, and home environment barriers to behavior change. Changes in sitting time and breaks from sitting will be compared between baseline, mid-intervention, and post-intervention measurement occasions.

**Specific Aim 3: Determine whether sedentary behavior intervention results in improved insulin sensitivity and glycemic control.** To evaluate whether reduced sitting results in meaningful metabolic changes, we will measure postprandial insulin and glucose, and body composition, and evaluate changes from pre- to post- intervention adjusting for relevant covariates.

The PI is an early-career investigator who has completed KU-ADC funded pilot work using objective activity monitoring and has the necessary foundation for the proposed research on physical activity and sedentary behavior in older age and AD. She has several published papers on biomarkers associated with cognitive decline and dementia. She has successfully collaborated with the KU-ADC since 2008 to build a program of research measuring physical activity in naturalistic settings in older adults with and without AD. She has experience in use, interpretation, and analysis of objective activity monitoring data in ADC participants. Her pilot work found that participants with mild AD did not differ from older adult controls in their levels of moderate physical activity, but differed in sedentary and light intensity activities. This supports the idea that sedentary behavior is a valuable target for this population.

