### **B. Study Type and Design:**

The proposed pilot study will include individuals with MCI and their caregivers as a dyad. We will use a multi-level model to evaluate the change in our outcome variables across three time points. Level 1 is time of observation (baseline, mid-study, follow up). Level 2 is the individual (with or without MCI), and Level 3 is the level of the dyad. This model includes the non-independence in the estimation of the two members of the dyad as well as repeated observations for each individual. This model also allows us to compare whether individuals with MCI are equally or less responsive to the intervention than the study partners within the context of the dyadic relationship. Future funding applications will include an RCT design with a control group of dyads who do not receive the intervention or a double baseline design to establish within person change with and without the intervention. We chose an intervention duration of 12 weeks. A previous intervention study in middle-aged adults observed changes in glucose and insulin within 2 hours of reduced sitting replaced by light walking. A 6-month intervention in adults improved insulin levels and waist circumference.

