We will use a multi-level model to evaluate the change in our outcome variables across three time points. Level 1 is time of observation (baseline, mid-study, follow up). Level 2 is the individual (with or without MCI), and Level 3 is the level of the dyad. This model includes the non-independence in the estimation of the two members of the dyad as well as repeated observations for each individual. This model also allows us to compare whether individuals with MCI are equally or less responsive to the intervention than the study partners within the context of the dyadic relationship. Constraining estimates to be equivalent provides a test of the significance of the difference in the estimates between the MCI patients and the study partners. We are primarily interested in the change in outcome measures (listed below) from pre-intervention to post-intervention (i.e., is the intervention effective), thus we are testing for a growth model with an intercept change, indicating a mean change after the intervention, this type of model can estimate discontinuous processes with longitudinal data. With regard to the multiple time points, we hypothesize an improvement in outcomes from baseline to mid-point and a maintenance effect from mid-point to follow up. Outcomes are (1) average daily sitting time (2) number of sitting bouts  $>30$  min (3) insulin and glucose, adjusting for baseline values and relevant covariates (disability status, medications, age, education, etc.). Data will be validated for wear time (i.e. remove periods of sleep or monitor removal). A valid day of wear is  $\geq 10$  hours of waking wear time and a valid week of wear includes  $\geq 4$  valid days of wear ( $\geq 1$  weekend day).

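### Insulin and glucose are measured twice, but the shared three-occasion model uses their baseline both as an outcome row and as a covariate, which makes the standard error of change slightly too small (minor)

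*Combined protocol and SAP*

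**What the plan says.** Section II.B (Study Type and Design) introduces a single model for everything: "We will use a multi-level model to evaluate the change in our outcome variables across three time points". The section on sample size and statistical methods and section V (Statistical and Data Analysis) repeat it and define the lowest level: "Level 1 is time of observation (baseline, mid-study, follow up". Baseline is thus one of the response rows.

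Both statistical sections then list the outcomes. The third is given as "3) insulin and glucose, adjusting for baseline values and relevant covariates (disability status, medications, age, education, etc". They state the target contrast, "We are primarily interested in the change in outcome measures (listed below) from pre-intervention to post-intervention", and a hypothesis about the path over time: "we hypothesize an improvement in outcomes from baseline to mid-point and a maintenance effect from mid-point to follow up". They also plan a comparison of roles, in which constraining estimates "provides a test of the significance of the difference in the estimates between the MCI patients and the study partners".

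Elsewhere the biomarker schedule is narrower. Table 2 marks insulin and glucose at the baseline clinic visit (V1) and the final clinic visit only. The final visit is V2 in the table and V3 in the text. The week 6 assessment described under Procedures is postural monitoring only. Specific Aim 2 assigns the three measurements to the monitors: "Electronic postural monitors will record sitting time for a duration of one week at three time" points. Specific Aim 3 says of the biomarkers that "we will measure postprandial insulin and glucose, and body composition, and evaluate changes from pre- to post- intervention", adjusted for covariates, and does not list the baseline value among them.

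**The concern.** In a mixed model for repeated measures, baseline can be a response, with change read from the occasion effect. Alternatively it can be a covariate, with only later values as responses. The shared text asks for both for insulin and glucose. With two occasions, half of the response rows are then the covariate itself. The fitted residuals no longer behave as the random-intercept structure assumes, and the interval for biomarker change is affected. The hypothesis of improvement by mid-point followed by maintenance is also worded for outcomes in general, but it cannot be examined where no mid-point sample exists.

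What is at stake is the precision reported for Aim 3. The protocol says that Aims 2 and 3 will concentrate on effect sizes, and that the results will support a larger grant application. The biomarker intervals should therefore be right, even in a pilot.

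**Working it through.** The documents give no power, alpha level or expected precision for the biomarkers, so there is no plan figure to reproduce.

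**Inputs.** From the protocol: 15 dyads, 30 people, two biomarker occasions. Assumed: complete data, equal variance (SD 1) at both occasions, pre-post correlation ρ of 0.5 to 0.8, and independent changes within dyads.

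**Step 1: rows.** The schedule yields 30 × 2 = 60 biomarker rows per outcome. The shared text implies 30 × 3 = 90.

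**Step 2: point estimates.** A person's baseline value is the same on both of that person's rows. With complete data it is orthogonal to the within-person occasion contrast. Adding it therefore leaves the change and role × occasion estimates unchanged. In simulation the two fits agreed to within 1e-14.

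**Step 3: residuals under the literal rule.** The regression on baseline has slope 1 on baseline rows and ρ on follow-up rows, so the pooled slope is (1 + ρ)/2.

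- Baseline residual variance: (1 − ρ)²/4.
- Follow-up residual variance: (1 − ρ)(5 + 3ρ)/4.
- Average of the two: (1 − ρ)(3 + ρ)/4.
- Covariance of a person's two residuals: −(1 − ρ)²/4.

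The covariance is negative, and a random person intercept can represent only a positive one. Its variance is therefore pushed to zero.

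**Step 4: standard error of change.** The correct value is √[2(1 − ρ)/30]. The literal model replaces (1 − ρ) by (1 − ρ)(3 + ρ)/4, so the ratio of literal to correct is √[(3 + ρ)/4].

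| ρ | Correct SE (SD units) | Ratio | Literal SE |
|---|---|---|---|
| 0.5 | √(1.0/30) = 0.183 | √(3.5/4) = 0.935 | 0.171 |
| 0.7 | √(0.6/30) = 0.141 | √(3.7/4) = 0.962 | 0.136 |
| 0.8 | √(0.4/30) = 0.115 | √(3.8/4) = 0.975 | 0.113 |

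**Step 5: simulation with REML, 15 complete dyads, independent changes.**

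| Random intercepts | SE ratio at ρ = 0.5, 0.7, 0.8 | Person variance estimated as zero |
|---|---|---|
| Person only | 0.937, 0.960, 0.976 | 97%, 88%, 77% |
| Person and dyad | 0.929, 0.947, 0.959 | 99%, 96%, 92% |

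The smallest shortfall is 1 − 0.976 = 2.4% and the largest is 1 − 0.929 = 7.1%, hence about 2 to 7%.

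A separate simulation (400 data sets per setting, within-dyad correlation 0.2) gave mean SEs of 0.180 with baseline as outcome only and 0.167 with baseline in both roles at ρ = 0.5. At ρ = 0.7 they were 0.142 and 0.134. Coverage of the 95% interval went from 95.0% to 93.2% and from 95.8% to 95.0%.

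**The case against.** The strongest reply is that the sponsor plainly intends a pre-post comparison and that the harm is slight. Aim 3, Table 2 and the sentence on the primary contrast all point that way. The variance that collapses is a nuisance parameter that nobody will report, and coverage falls by only one or two percentage points. All of this stands, and it is why the point is minor. It does not remove the conflict, because the two statistical sections still instruct the analyst to use baseline twice and nothing elsewhere overrides them.

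A second reply is that the baseline adjustment may be loose wording. It could mean that the model intercept carries the starting level, or that only follow-up values are modelled with baseline as covariate. Both readings are coherent, but neither is stated. The follow-up-only model also recovers mean change if baseline is centred. Its MCI-partner comparison, however, is no longer a difference in change. Roles are not randomised, and the background section says that people with MCI differ in insulin and glucose regulation. With no true change, a stable baseline gap shifts that contrast by (1 − ρ) × gap. For an assumed gap of 0.5 SD and ρ = 0.7, this is 0.3 × 0.5 = 0.15 SD. This is a reason to prefer baseline as an outcome. It does not show that the planned contrast is biased, because the reading, the gap and ρ are all assumed, and the glucose eligibility limits may keep the gap small.

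A reader might also infer a much larger understatement of the SE, on the ground that partners are treated together and their changes may correlate. Most of that would come from omitting a dyad × occasion random effect. That is a separate, optional modelling choice, and the documents give no value for the correlation.

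**Conclusion.** The point holds as a minor error in the text as written. Baseline insulin and glucose are given two incompatible roles in a model whose three-occasion wording does not fit two-occasion data. The consequence is an SE of biomarker change about 2 to 7% too small, under complete data, ρ between 0.5 and 0.8, and independent changes within dyads. Incomplete data were not examined.

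A reader might infer that the biomarker effect estimates are biased. They are not: with complete data they are identical under either fit. Nor is a mid-study blood sample missing, since the documents consistently plan two. Aim 1 and the sitting target are untouched. The protocol judges effectiveness on sitting, and it already calls Aims 2 and 3 underpowered.

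**What to change.** In both statistical sections, delete the adjustment for baseline values from the insulin and glucose outcome, so that baseline is a response row only. Then add a statement along these lines: insulin and glucose outcomes have two occasions, the baseline and follow-up clinic visits, and are analysed by a linear mixed model with role, occasion, role × occasion, the planned covariates, and random person and dyad intercepts. This matches Aim 3, and it keeps the MCI-partner test a difference in change.

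In section II.B and both statistical sections, restrict the three-time-point wording and the mid-point and maintenance hypothesis to the sitting outcomes.

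The cost is a few sentences, with no new data, visits or participants. Reported biomarker intervals become slightly wider because the understatement is removed.

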**Preliminary Results:** The PI is an early-career investigator with a foundation for the proposed research on physical activity, sedentary behavior, and associated biomarkers in older age and AD. Pilot research allowed us to establish expertise in use, interpretation, and analysis of activity monitoring data. In 100 participants, we had excellent retention (99%) and low rates of technological problems that prevent valid data collection (5%). We found that participants with mild AD did not differ from older adult controls in their levels of moderate physical activity, but differed in sedentary and light intensity activities. This supports the idea that sedentary behavior is a valuable target for this population. We discovered that patterns of activity variability differ between men and women (i.e., women are more consistently active across days), but did not differ by dementia status. Understanding within-individual variability helps target interventions toward individual habits to result in tailored behavior change approaches. We conducted a focus group with the KU-ADC Ambassadors and consulted with experts ([name], [name], [name], [name], & [name]) to develop our intervention.

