## Sample Size, Statistical Methods, & Power

We will enroll 15 dyads of older adults (N=30 individuals; 15 with MCI and 15 non-impaired caregivers).

Aim 1: We will evaluate feasibility in terms of 1) successful recruitment and retention of participants, specifically how many months did it take to recruit an adequate sample of participants, 2) 10% or less of technological failures, calculated as the number of failures divided by the total number of participants enrolled, 3) rate of participant concerns addressed by phone and at home visits, as measured by numerical counts of concerns successfully or unsuccessfully addressed and percent of participants having concerns, and 4) acceptability of the intervention to participants (measured by questionnaires during home visits), we will describe these data using descriptive statistics.

Aims 2 and 3: Our proposal is underpowered to detect significant effects, however we will focus on finding a meaningful effect size for the treatment (which is not affected by sample size). We feel this is acceptable given the **feasibility** focus of our pilot study. A previous RCT of an intervention to reduce sitting in multiple sclerosis reported a statistically significant main effect, Cohen's  $d = 0.49$ , for intent-to-treat analysis.

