Both members of the dyad will receive a water resistant activity monitor to wear on the non-dominant wrist (Jawbone Up, San Francisco, CA). Monitors will be programmed to provide vibrations ("idle alerts") to encourage activity after inactive periods of >30 minutes and to shut off during hours when participant is normally asleep. We chose Jawbone for programmability and vibration reminders (vs. auditory). Jawbone batteries last 10 days. Participants and study partners will be trained in their home on how to recharge them and can be assisted via telephone and during home visits if needed. Participants and study partners will indicate in logs during which activities they most frequently received alerts to assist in goal setting during subsequent visits.

TI1 (wk2) will focus on problems and adherence with idle alerts, monitor wear, success of limiting sitting to 30 minutes, and goals for other cues to limit sitting. HI1 (wk5) will focus on setting goals for replacing sitting with standing/light activity, maintenance of goals, and reduction of barriers. Study staff will attach activPAL monitors for mid-intervention assessment of changes in sitting time in both partners (**M**) measured during week 6 of the intervention. After the weeklong assessment, participants will mail monitors in a pre-addressed stamped padded envelope. TI2 (wk8) will check on success of goal maintenance and barrier reduction. HI2 (wk12) will be the final follow up visit to address barriers and discuss progress toward

maintaining goals. Questionnaires will be used to assess the acceptability of the intervention to participants. Study staff will attach activPAL monitors for post-intervention assessment of changes in sitting time (measured week 13).

**Follow up (V3).** Participants will return monitors to the clinic and complete follow up biomarker testing (glycemic control, insulin resistance, BMI, and waist circumference). Participants will receive feedback from postural monitoring during the waiting period of glucose testing.

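### Acceptability appears to be rated only at the week-12 home visit, and nobody is asked on withdrawal, so the figure would be too favourable if dissatisfied participants leave early

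*Combined protocol and SAP*

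**What the plan says.** Four places describe when acceptability is measured.

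- Section V, Statistical and Data Analysis, names one visit: "acceptability of the intervention to participants (measured by questionnaires HI3"). In Table 2, HI3 is the week-12 home visit, the last of three.
- Section II.E, Procedures, describes week 12 as follows: "HI2 (wk12) will be the final follow up visit to address barriers and discuss progress toward" maintaining goals. The next sentence reads "Questionnaires will be used to assess the acceptability of the intervention to participants". No other visit description mentions the questionnaire. The label here is HI2, which Table 2 gives to the week-5 visit.
- The section on sample size, statistical methods and power, under Aim 1, says "acceptability of the intervention to participants (measured by questionnaires during home visits") and names no visit.
- Specific Aim 1 in section I.A uses the same general wording.

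Table 2 has no questionnaire row. The planned analysis is descriptive: "measured by questionnaires during home visits), we will describe these data using descriptive statistics". No scoring rule, threshold, denominator or missing-data rule for acceptability is stated. Section III.D lets participants withdraw at any time. The available text describes no exit questionnaire and no recording of reasons for leaving.

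**The concern.** Wrist alerts and intervention visits begin in week 1, about 11 weeks before the only rating that is tied to a visit. Someone who stops because the alerts are intrusive or the visits unwelcome would be missing from the rating because of the very thing being rated. What remains is the opinion of those who stayed.

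This matters because the study's stated purpose is feasibility, acceptability is one of its milestones, and section V says the results will support an application for a larger randomised trial. Partners receive the intervention together, so losses may come in pairs, and each dyad is 2/30 = 6.7% of the sample. The views of early leavers may not be recoverable once the study has ended.

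**Working it through.** **Timing.** Both places that tie the questionnaire to a visit point to week 12: section V through the HI3 label and Table 2, and the Procedures through the week stated in the text. The HI2 label in the Procedures looks like a slip, because the same sentence gives week 12 and calls the visit the final one. The two general statements could mean several visits. Even then, someone who leaves between visits is not asked at departure.

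**Inputs from the documents.** The sample is given as "We will enroll 15 dyads of older adults (N=30 individuals; 15 with MCI and 15 non-impaired caregivers"), and 15 x 2 = 30 is consistent. The plan states no acceptability or dropout figure for this intervention, so there is none to reproduce.

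**Assumed inputs (not in the documents).** p is the proportion of completers who accept, 90% or 80%. L is the number of individuals lost before week 12: 0, 2, 4 or 6, that is, 0 to 3 whole dyads. q is the proportion of leavers who accept: none, half, or the same as completers.

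**Formulas.**

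Acceptability over all enrolled = [p(30 - L) + qL] / 30

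Bias of the completers-only figure = p minus the above = (L/30)(p - q)

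The bias formula also holds for a mean score, with means in place of p and q.

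**Results.**

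| Dyads lost (L) | p = 90%, q = 0 | p = 90%, q = 50% | p = 80%, q = 0 | p = 80%, q = 50% |
|---|---|---|---|---|
| 0 (0) | 90.0% | 90.0% | 80.0% | 80.0% |
| 1 (2) | 84.0% | 87.3% | 74.7% | 78.0% |
| 2 (4) | 78.0% | 84.7% | 69.3% | 76.0% |
| 3 (6) | 72.0% | 82.0% | 64.0% | 74.0% |

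Example, 2 dyads lost and p = 90%: 0.9 x 26/30 = 78.0% if no leaver accepts; (23.4 + 2)/30 = 84.7% if half do. The bias is 12.0 or 5.3 points. If q = p, the bias is zero at any L.

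**How likely is any loss?** Section I.B reports from pilot activity monitoring: "In 100 participants, we had excellent retention (99%) and low rates of technological problems". If 99% retention held here, the expected loss is 0.01 x 30 = 0.3 people, the chance of losing at least one is 1 - 0.99^30 = 26% (assuming independence), and the expected bias is at most about 1 point. With assumed dyad dropout of 5%, 10% or 20%, the chance of losing at least one of 15 dyads is 1 - 0.95^15 = 54%, 1 - 0.90^15 = 79% or 1 - 0.80^15 = 96%.

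**The case against.** The strongest reply is that dissatisfied leavers are not invisible. Retention is a separate milestone, so every departure counts somewhere. Participant concerns are another: the plan counts those resolved and unresolved, and the share of participants who have any. The week-2 call deals with problems with the alerts, and later contacts deal with barriers, so a complaint may be on record before the person leaves. This stands, but only in part. The sample size section makes the recruitment and retention item specific only as the time needed to recruit, with no retention rate. Concerns are recorded through calls and home visits that a leaver no longer has. Neither milestone records why someone left.

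A second reply is that a 12-week programme is reasonably rated at its end. That also stands. A week-5 rating would precede much of the intervention, and its absence is not a fault.

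A third is that leaving need not reflect dissatisfaction. People may go because of illness or family circumstances, and then no bias of this kind need arise. That is correct, and the conclusion must stay conditional.

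A reader might go further and infer that the milestone passes by construction. The documents do not support this: there is no acceptability threshold and the data are to be described only, so no pass/fail result can be shown to change. A reader might also infer that the plan relies on 99% retention here. It does not. That figure is offered as experience with monitoring, not as a dropout assumption.

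**Conclusion.** The point holds in conditional form. The timing is stated inconsistently, the statements that can be tied to a visit all lead to week 12, and no reading covers people at withdrawal. If some participants leave because they dislike the intervention, the completers-only figure will be too high.

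Its size is modest for one dyad lost (3 to 6 points when 90% of completers accept) and material for three (8 to 18 points). These ranges rest on assumed dropout and completer rates and on a yes/no reading of a questionnaire whose scoring is not given. The upper ends are worst cases in which no leaver accepts. The bias vanishes with no loss, or if leavers rate the intervention as completers do.

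A reader might take it as settled that the questionnaire is given only at week 12, or that the milestone is biased as it stands. The first goes beyond documents that elsewhere speak of home visits in general. The second presupposes dissatisfied dropout, which nothing in the documents establishes. This is a gap in collection and reporting that should be closed because doing so is cheap. It does not undermine the study.

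**What to change.** - Keep the week-12 questionnaire. Give the same questionnaire by telephone at withdrawal and record the reason for leaving. A week-5 administration is optional.
- Report acceptability with all enrolled as the denominator, as counts accepting, not accepting and not responding, beside the retention rate. State whether people replaced under section II.D stay in the denominator.
- Add a sensitivity analysis that counts non-responders as not accepting, labelled as a worst case.
- Make Specific Aim 1, the sample size section, the Procedures and section V agree on timing. Correct the HI2/HI3 label against Table 2 and add a questionnaire row to that table.

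The cost is a short call to each person who withdraws, some of whom may decline, and probably a slightly less favourable acceptability figure. No extra visit is needed.
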